Specific Aim 1. We will recruit 15 runners; ten with unilateral and five with bilateral transtibial amputations that currently use and have at least one year of experience with distance-running RSPs. Subjects will be between 18-55 years old and have no current problems with their prosthesis or residual limb. There will be no restrictions on sex, race, or ethnicity for inclusion. Subjects will be at a K4 Medicare Functional Classification Level, which is defined as a person who has the ability or potential for prosthetic ambulation that exceeds basic ambulation skills, exhibiting high impact, stress, or energy levels. Subjects will have no known cardiovascular, pulmonary, or neurological disease or disorder. These inclusion/exclusion criteria will minimize any potential confounding variables, thereby increasing the internal validity of the proposed studies. Any person matching the inclusion criteria of the study, regardless of race or gender, will be recruited to participate.

Specific Aim 2. We will recruit 15 sprinters; ten with unilateral transtbial amputations and five with bilateral transtibial amputations that currently use and have at least one year of experience with sprint-running RSPs. Subjects will be between 18-55 years old and have no current problems with their prosthesis or residual limb. There will be no restrictions on sex, race, or ethnicity for inclusion. Subjects will be at a K4 Medicare Functional Classification Level, which is defined as a person who has the ability or potential for prosthetic ambulation that exceeds basic ambulation skills, exhibiting high impact, stress, or energy levels. Subjects will have no known cardiovascular, pulmonary, or neurological disease or disorder. These inclusion/exclusion criteria will minimize any potential confounding variables, thereby increasing the internal validity of the proposed studies. Any person matching the inclusion criteria of the study, regardless of race or gender, will be recruited to participate.

[figure not shown]

Figure 2. Overview of the experimental design. We will vary distance-running RSP (*Specific Aim 1*) and sprint-running RSP (*Specific Aim 2*) stiffness (k) and height (h) to create guidelines for prosthetic prescription.

C. Study Design and Research Methods

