The study will be a repeated-measures design. We will calculate subject and group averages for each condition from data normalized to a gait cycle. The data analyzed will include: leg stiffness, peak vertical and horizontal ground reaction forces, stance time, leg swing time, metabolic costs, top speed, peak socket pressure, and maximum socket motion. We will use repeated measures analysis of variance (ANOVA) to compare each variable across all conditions. Any significant differences will be further analyzed with either a Tukey HSD or Newman-Keuls follow-up procedure. In the case of an unequal number of subjects, we will use a Sheffe follow-up procedure. We will use p < 0.05 as a criterion for determining statistical significance. All statistical analyses will be performed with JMPIN software (JMPIN, SAS Institute, Cary, NC).

Specific Aim 1. Subjects will complete six experimental sessions at the University of Colorado Locomotion Lab; each session on a separate day and requiring approximately two hours of time. During each experimental session, subjects will run at two speeds, the speed required for their age/sex 50th percentile PFT (Physical Fitness Test) 2 mile run and a standard speed of 3 m/s on a force measuring treadmill while we measure their ground reaction forces, metabolic demand, socket pressures, and socket pistoning. Subjects will run with three different brands (Ossur,

Ottobock, and Freedom Innovations) of distance-running RSPs with three different stiffnesses at one height and three different heights at one stiffness of each brand, a total of five or more different conditions per brand at two speeds. Individual trials will be five minutes long with at least 2 minutes rest between trials.

Day DR0: Subjects will be asked to give informed written consent and then will be fit and aligned by a certified prosthetist with three different distance-running RSP brands, one from each company. We will measure each subject's height, weight, and limb segment lengths. Then, we will select an RSP stiffness category based on the subject's weight and manufacturer's recommendation. An appropriate RSP height for each subject will be chosen according to conventional practice. Our prosthetist will ensure that the prosthetic fit and alignment are adequate. Then, subjects will have time to accommodate to treadmill running with each distance-running RSP.

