All investigators obtaining consent will have completed all VA and COMIRB mandatory annual training. Subjects will be allowed to read the consent form in a private and quiet room with just the investigator(s) present. All potential participants will be given adequate time to read the consent form. After the subject reads the consent form, an investigator will ask them if they have any questions, and answer any questions. The investigator will then follow-up with a few questions to ascertain whether the subject actually read and understood the consent form. If the subject's responses seem vague, the investigator will ask the subject to re-read the consent form and the investigator will explain any uncertainties. Consent will take less than 15 minutes and will be obtained immediately prior to the first session of the experiment.

Potential Risks.

- 1. There is a small risk of falling during the experimental trials.
- 2. There is a potential risk of physical discomfort from wearing any type of prosthesis.
- 3. The adhesive used for socket pressure and socket pistoning measurements may produce slight discomfort/irritation.
- 4. The metabolic analysis mouthpiece may produce slight discomfort/irritation.
- 5. Confidential information will be collected as part of this study; therefore there is a risk of disclosure.

Protections against Risks (corresponds directly to the Potential Risks listed above).

- 1. Subjects will have access to parallel bars on the treadmill and an overhead safety harness in case they need to catch themselves in the unlikely event of a fall.
- 2. If a subject becomes fatiqued, he/she may ask to rest or stop the study at any time.
- 3. Before participating, all subjects will be asked if they have any adhesive or latex allergies. If they do, we will use a non-latex tape.
- 4. Subjects may ask to remove the mouthpiece, rest or stop at any time.
- 5. Significant efforts will be made to guard against the disclosure of confidential information. We will use de-identifying codes for all data and will implement a data and safety-monitoring plan to ensure subject's privacy.

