In Specific Aim 1, we propose to have subjects complete a total of six running trials per day and each trial will last 5 minutes. In Specific Aim 2, we propose to have subjects complete three sets of running and sprinting trials from 3 m/s up to top speed and each trial will last approximately 30 seconds. The proposed experimental trials may be too difficult, long, and/or exhausting. However, we have previously conducted up to eight running economy trials without detecting any effects of fatigue (Grabowski & Kram, 2008; Teunissen, Grabowski, & Kram, 2007). Moreover, our previous studies of Paralympic athletes with transtibial amputations suggest that subjects can complete three sets of running and sprinting trials from 3 m/s up to top speed without showing effects of fatigue (Grabowski et al., 2010). Thus, we believe that our proposed experimental protocol will be adequate; however if we do see signs of fatigue, we may need to spread out the protocol over more days.

We expect to find that for some subjects the optimal stiffness is either softer or stiffer than the manufacturer's recommended stiffness or that the optimal height is taller or shorter that the traditionally recommended height. Therefore, it may be necessary to add conditions to our protocol so that we can establish the true minimum metabolic cost or maximum speed. On Days 2, 4, and 6, we would be able to test an additional stiffness and height condition without exceeding the recommended number of trials per session. If additional trials are necessary, we may need to add an additional day to our protocol.

F. Data Analysis Plan:

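### A missed setting either drops the subject from a classical repeated measures ANOVA or leaves condition averages taken over different people; the stated Scheffé follow-up test corrects neither

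*Combined protocol and SAP*

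**What the plan says.** All of the statistical method is in the opening paragraph of section IV.C, Study Design and Research Methods. It describes a repeated measures design and the summary: "We will calculate subject and group averages for each condition from data normalized to a gait cycle". It then plans a repeated measures ANOVA for each variable over all conditions, with Tukey HSD or Newman-Keuls follow-up. For unequal numbers it says: "In the case of an unequal number of subjects, we will use a Sheffe follow-up procedure".

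Section IV.F is titled Data Analysis Plan but covers confidentiality and data storage. Neither section gives an analysis set, a rule for withdrawn subjects or missed settings, or a sensitivity analysis.

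The load per subject is also in IV.C. For Aim 1: "Subjects will complete six experimental sessions at the University of Colorado Locomotion Lab; each session on a separate day", with "a total of five or more different conditions per brand at two speeds" for each of three brands. Aim 2 has the same six sessions and the same minimum of five conditions per brand. In both aims the investigators may add a stiffness category or 1 cm height steps where the data suggest it, and IV.E repeats this possibility.

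On stopping, IV.D says of a fatigued subject that "he/she may ask to rest or stop the study at any time". IV.E says "if we do see signs of fatigue, we may need to spread out the protocol over more days".

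**The concern.** Incomplete data can arise in two ways. A subject may stop or miss a setting during six demanding days. Or a subject may be given an optional setting that others are not, which unbalances the data even if nobody leaves.

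A classical repeated measures ANOVA needs every cell for every subject, so one gap removes that subject from the group comparison, including within-person contrasts that were fully observed. Raw condition averages keep the subject where data exist, but the averages being compared then come from different sets of people. Part of any difference between settings is then a difference between subjects. With 15 subjects per aim, five of them bilateral, one or two people can move an average noticeably.

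A follow-up test acts after the averages and the error term have been formed, so changing the test cannot repair either problem.

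**Working it through.** The documents state no power calculation, SD or dropout rate, so there is no figure to reproduce. All rates and SDs below are assumptions.

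**Inputs from the documents**
- Subjects: 15 per aim. Aim 1: "We will recruit 15 runners; ten with unilateral and five with bilateral transtibial amputations". Aim 2: "We will recruit 15 sprinters; ten with unilateral transtbial amputations and five with bilateral transtibial amputations" (IV.B).
- Test days: 6 per aim, after the fitting day (IV.C).
- Settings: at least 5 per brand × 3 brands = 15 per subject.

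**1. Subjects left in a complete-case analysis**

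With stopping rate p per session, the fraction complete is (1 − p)^6. With independent misses at rate q per setting, it is (1 − q)^15. The standard error grows by 1/√(fraction complete).

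| Assumption | Fraction complete | Expected of 15 | SE increase |
|---|---|---|---|
| p = 2% per session | 0.98^6 = 0.886 | 13.3 | 6% |
| p = 5% per session | 0.95^6 = 0.735 | 11.0 | 17% |
| q = 2% per setting | 0.98^15 = 0.739 | 11.1 | 16% |
| q = 5% per setting | 0.95^15 = 0.463 | 6.9 | 47% |

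The per-session rows fit withdrawal better. The per-setting rows overstate the loss if misses cluster within a few subjects.

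The chance that at least one of 15 subjects is incomplete is 1 − (fraction complete)^15. At 1% per session it is 60%, and at 2% it is 84%.

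**2. Shift in a raw condition average**

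- If one subject lying z SD from the group mean is missing, the average moves by z/(n − 1) SD. For z = 2 this is 2/14 = 0.14 SD in all 15, and 2/4 = 0.50 SD among the five bilateral subjects.
- If the three lowest of 15 are missing from a setting, simulation gives a shift of 0.33 between-subject SD.
- A second simulation assumed no true effect, between-subject SD 1 and within-subject SD 0.3, with the three highest subjects missing one brand. The difference in raw averages was −0.33 SD. The within-subject contrast among the 12 who had all brands was 0.00. The mixed model itself was not fitted; this contrast is what it targets.
- If three random subjects are missing instead, the raw difference is unbiased, but its SD rises from 0.042 with complete data to 0.138.

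**3. What Scheffé changes**

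The 5% critical values for a pairwise difference are √((k − 1)F) for Scheffé and q/√2 for Tukey, where q is now the studentized range quantile. With k = 15 conditions and 14 subjects (error df 14 × 13 = 182) they are 4.95 and 3.44. With k = 3 they are 2.60 and 2.49. The switch widens intervals. It does not bring back a dropped subject or alter any average.

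**The case against.** The strongest reply is that the plan never states listwise deletion. A repeated measures ANOVA fitted as a linear model with subject as a factor would keep incomplete subjects and compare within person. That is true, and it is why the point is limited to the classical form. But the plan does not specify such a fit, and it does name raw group averages.

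The Scheffé sentence may refer only to the ten/five split. If so, it was never meant as a missing-data rule, and the plan has no analysis response to missed settings.

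Four stronger readings are tempting, and the documents do not support them.

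- *Scheffé is the plan's only response of any kind.* IV.E allows extra days, and IV.C gives Aim 2 subjects full recovery time between trials. Both should reduce missed settings. Scheffé is the only analysis response.
- *A subject who leaves after Day 4 contributes nothing.* Both hypotheses concern the optimum for each subject, and optima are found brand by brand. Two completed brands give usable optima. The loss is to the group comparison.
- *The bias falls on one brand.* IV.C does not state the order of brands. The shift attaches to one brand only if the order is the same for all subjects.
- *IV.D and IV.E contradict each other on fatigue.* They do not. One is a subject's right to rest or stop, the other a scheduling option for the investigators, and both can apply.

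The sponsor can also cite favourable experience: more than 15 sprinters tested without incident (IV.D) and no fatigue effects in earlier sessions (IV.E). That supports the lower assumed rates. It does not show that subjects complete six days, and it does not bear on the optional settings.

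**Conclusion.** The concern holds in this limited form. The stated analysis does not handle unbalanced data, which are likely from the length of the schedule and the optional settings, and Scheffé does not address the problem.

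Under the milder per-session assumption the cost in precision is modest: standard errors about 6% to 17% larger at 2% to 5% stopping. Scattered misses at the same rates would leave about 11 or 7 complete subjects. The possible bias in a raw average reaches 0.33 between-subject SD if the three most extreme subjects on one side are lost. That is an unfavourable case, not an expected one. Random loss gives no bias but a noisier comparison.

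None of these rates comes from the documents. The defect does not depend on them; only its size does. The individual optima from completed brands are not in doubt.

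**What to change.** In section IV.C, replace the classical ANOVA and the Scheffé sentence with the following.

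- A linear mixed model for each variable, fitted by REML, with a random subject effect. Fixed effects are setting and brand, plus speed in Aim 1. Every completed setting from every subject is used, with optional settings given their own defined levels.
- Model-based within-subject differences between settings as the main result, with a Tukey-type adjustment of the contrasts and the number of subjects shown for each setting.
- A completers-only sensitivity analysis.
- A recorded reason for each missed setting.

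No change to the stopping or scheduling text in IV.D or IV.E is needed for this point.

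The cost is analysis wording and one data field, with no extra subjects or procedures. The output is slightly more complex than an ANOVA table. The model also assumes that missingness is explained by the observed data, so the reasons for missed settings and the completers-only analysis should be reported beside it.

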We do not yet know how prosthetic stiffness affects overall leg stiffness while running and sprinting. During running in non-amputees, the overall biomechanics of the body are wellcharacterized and predicted by a spring-mass system that represents the body's mass as a point mass and the legs as mass-less linear springs (Blickhan, 1989; Brughelli & Cronin, 2008; Farley & Ferris, 1998; Farley, Glasheen, & Mcmahon, 1993; He, Kram, & McMahon, 1991; McMahon & Cheng, 1990). During the first half of the stance phase of running, the kinetic and gravitational potential energies of the body are stored as elastic energy in the leg. During the second half of the stance phase, this elastic energy is returned to the body. At slow to moderate speeds (2-6 m/s), previous studies have shown that leg stiffness is independent of speed in non-amputees (Farley et al., 1993; He et al., 1991; McGowan et al., 2012; Morin, Dalleau, Kyrolainen, Jeannin, & Belli, 2005). Thus, an optimal distance-running RSP stiffness for an individual with a unilateral amputation would be expected to result in an overall affected leg + prosthesis stiffness that is equal to the overall unaffected leg stiffness. This optimal stiffness would likely minimize biomechanical asymmetry and metabolic demand. At speeds greater than 6 m/s, non-amputee runners progressively increase their leg stiffness with speed (McGowan et al., 2012). Thus, it is probable that a stiffer prosthesis is required to maximize top speed (McMahon & Greene, 1979). Given that the biological leg spring compresses by only 2.0-2.5 cm during the stance phase of running (Farley & Gonzalez, 1996; McGowan et al., 2012), changing the height of an RSP by just one cm could also profoundly affect the dynamics of the spring mass model.

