Day DR1: We will first vary the distance-running RSP stiffness (k) while keeping height (h) at the traditionally recommended level. Subjects will use an RSP with the manufacturer's recommended stiffness category based on their weight, an RSP that is one category softer (k-) and an RSP that is one category stiffer (k+) than the manufacturer's recommended stiffness. We will measure ground reaction forces, metabolic demand, socket pressures, and socket pistoning while subjects run at the speed required for their age/sex 50th percentile PFT (Physical Fitness Test) 2 mile run and at 3 m/s, a total of six trials. If the data warrant it, we may add an additional stiffness category to further fine tune the optimal stiffness. The optimal stiffness (k_{opt}) distance-running RSP will be the RSP that minimizes metabolic cost. This RSP stiffness will be used for Day DR2.

 $\underline{\text{Day DR2:}}$ We will keep RSP stiffness constant (k_{opt}) and vary the distance-running RSP height (h). Subjects will have used an RSP with an optimal stiffness (k_{opt}) at the recommended height (h_R) on day Day DR1. On Day DR2, they will also use and RSP with an optimal stiffness (k_{opt}) that is 2 cm shorter (h-), and 2 cm taller (h+). We will measure ground reaction forces, metabolic demand, socket pressures, and socket pistoning while they run at their PTF speed and at 3 m/s; a total of four trials. If the data warrant it, we may further fine tune RSP height in 1 cm increments. We will analyze the results of DR2 to identify the optimal height (h_{opt}) for each subject for one brand of a distance-running RSP.

Days DR3 and DR5: We will repeat the trials of Day DR1 and vary stiffness (k) for a different distance-running RSP brand. We will analyze the results of Days DR3 and DR5 to identify the optimal RSP stiffness (k_{opt}) to be used for Days DR4 and DR6.

Days DR4 and DR6: We will repeat the trials of Day DR2 and vary height (h) for a different distance-running RSP brand. We will analyze the results of Days DR4 and DR6 to identify the optimal height (hoot) for each subject using the respective brand of a distance-running RSP.

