Specific Aim 2. Subjects will complete six experimental sessions at the University of Colorado Locomotion Laboratory; each session on a separate day and requiring approximately two hours of time. During each experimental session, subjects will run and sprint over a range of speeds, from 3 m/s up to top speed on a force measuring treadmill while we measure their ground reaction forces, socket pressures, and socket pistoning. Subjects will run with three different brands (Ossur, Ottobock, and Freedom Innovations) of sprint-running RSPs with at least three different stiffnesses at one height and three different heights at one stiffness of each brand, a total of five or more different conditions per brand. Individual trials at each speed will be approximately 15-30 seconds long with at least 2 minutes rest between trials.

A safety harness attached to the ceiling above the treadmill and handrails beside the treadmill will be used during all running/sprinting trials to ensure subjects' safety. Each running trial will consist of at least 10 strides. To begin each trial, subjects will lower themselves from the handrails on to the moving treadmill belt. For each prosthetic stiffness and height condition, subjects will start a series of trials at 3 m/s, each subsequent trial will be incremented by 1 m/s until subjects approach their top speed, and then smaller speed increments will be employed until subjects reach their top speed. *Top speed* will be determined when subjects put forth maximal effort but cannot maintain their position on the treadmill for ten strides (Weyand, Sternlight, Bellizzi, & Wright, 2000). Subjects will be given as much time between trials as needed to recover fully (at least 2 minutes). At least seven trials will be performed by each subject for each prosthetic condition (e.g. 3, 4, 5, 6,

7, 7.3, 7.5 m/s) and a maximum of three series of trials will be performed each day. Our results will allow us to determine the optimal RSP mechanical stiffness (k_{opt}) and height (h_{opt}) for each person. The optimal sprint-running (SR) RSP will be the prosthesis that maximizes top speed.

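### Stiffness is chosen only at the recommended height and height only at that stiffness, so the design cannot show that the resulting pair is the optimal stiffness and height

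*Combined protocol and SAP*

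**What the plan says.** Section IV.C sets out the same sequence for both aims.

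- Specific Aim 1 plans, for each of three brands, "three different stiffnesses at one height and three different heights at one stiffness of each brand", which it counts as "a total of five or more different conditions per brand at two speeds".
- Day DR1 varies stiffness "while keeping height (h) at the traditionally recommended level". The best of these, k_opt, is the "distance-running RSP will be the RSP that minimizes metabolic cost. This RSP stiffness will be used for Day DR2".
- Day DR2 holds stiffness at k_opt and adds heights 2 cm below and 2 cm above the recommended height (h_R). The best of the three heights is h_opt.
- Days DR3–DR6 repeat this for the other two brands. Days SR1–SR6 follow the same layout for sprinting, with top speed as the criterion.

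The claims are about the pair. Hypotheses 1 and 2 (section I) concern the optimal stiffness and height for each subject. Specific Aim 2 says "Our results will allow us to determine the optimal RSP mechanical stiffness", together with height, for each person. Section IV.D promises each subject a recommendation of their best prosthesis. Section IV.E speaks of establishing the true minimum cost or maximum speed, and section IV.G promises prescription algorithms for both settings.

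There is some flexibility. If the data warrant it, a stiffness category or 1 cm height steps may be added. Section IV.E notes room for one more stiffness-height condition on Days 2, 4 and 6, or for an added day. No rule says which combination that condition should be.

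**The concern.** Choosing one factor at a time is guaranteed to find the best pair, measurement error aside, only when the best stiffness is the same at every height. The plan neither states this assumption nor tests it. Section III gives a reason not to take it for granted: it models running as a spring-mass system and says that "changing the height of an RSP by just one cm could also profoundly affect the dynamics of the spring mass model", while the tested steps are 2 cm. Section IV.E expects that for some subjects the best height will differ from the recommended one. For those subjects, stiffness will have been chosen at a height other than the one recommended to them.

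The title question, both hypotheses, the recommendation given to each subject and the prescription algorithm all depend on this step. If stiffness and height interact, an untested pair may be better than the reported one, and no required step would reveal it.

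**Working it through.** **Reproducing the plan's count.** Inputs from section IV.C: 3 stiffnesses, 3 heights, 2 speeds and 3 brands in Aim 1.

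- Conditions per brand: 3 + 3 − 1 shared (k_opt at h_R) = 5, as stated.
- Day DR1: 3 × 2 = 6 trials, matching "at 3 m/s, a total of six trials". Day DR2: 2 new heights × 2 = 4 trials, also as stated.

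**What is not run.** The grid has 3 × 3 = 9 cells, so 9 − 5 = 4 are untested: the two non-selected stiffnesses at each of the two non-recommended heights. Within one subject and brand, main effects need 1 + 2 + 2 = 5 parameters, which uses all 5 cells. None of the (3 − 1)(3 − 1) = 4 interaction degrees of freedom can be estimated.

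**Size, by illustration.** The documents give no response surface, so this one is assumed. In units of one tested step, cost = (k − k*)² + (h − h*)² + 2r(k − k*)(h − h*) on the grid {−1, 0, 1}². The true optimum (k*, h*) is uniform within R steps of the recommended setting, and there is no measurement error. The stepwise choice is compared with the best of the nine cells over 400,000 surfaces per case. Gain means the improvement over the recommended setting.

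| r | Best cell missed (R = 1 to 1.5) | Share of achievable gain kept (R = 1; R = 1.5) |
|---|---|---|
| 0 | 0% | 100%; 100% |
| 0.2 | 9–10% | 96%; 99% |
| 0.4 | 18–20% | 88%; 95% |
| 0.6 | 27–30% | 83%; 91% |

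**With noise.** Each condition is one trial per speed in Aim 1 and one series in Aim 2, so noise matters. With an assumed noise SD of 0.5 and R = 1.5, the rule misses the best cell in 33% of cases at r = 0, and in 35%, 39% and 45% at r = 0.2, 0.4 and 0.6. The part due to interaction is then 35 − 33 = 2, 39 − 33 = 6 and 45 − 33 = 12 percentage points.

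**Effect of one extra cell.** Suppose the runner-up stiffness is run at h_opt whenever h_opt is not h_R, and the better of the two is kept. Noise-free misses fall from 18–20% to 4–10% at r = 0.4, and from 27–30% to 14–26% at r = 0.6.

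**Why the planned cells cannot be pooled to estimate the interaction.** With h_R coded 0, the product k × h is zero on every stiffness day. On height days each subject-brand set has a single stiffness, k_opt. The interaction is therefore identified only by comparing height slopes between sets with different k_opt. On the assumed surface, treating stiffness as continuous, k_opt = k* + r·h*. The height slope at k_opt is −2h* + 2r(k_opt − k*) = −2(1 − r²)h*. For r > 0, a larger h* raises k_opt and lowers the slope, so the association is negative although the true coefficient, 2r, is positive. On the grid at R = 1.5, regressing height slope on k_opt gives about −0.3, −0.55 and −0.74 where the true values are +0.4, +0.8 and +1.2.

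**The case against.** The strongest case on the other side has four parts.

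- **The sequence is stated openly.** A reader of Days DR1–DR2 can see that each choice is conditional. This stands, but the claims in sections I, IV.D, IV.E and IV.G do not carry the condition with them.
- **Section IV.E allows a further condition and even another day.** This softens the problem. It is discretionary and has no rule for which cell to run, and the fine-tuning described on the study days moves along one factor at a time. One condition per height day covers at most 1 of the 4 untested cells.
- **A full grid would be a heavy burden.** It would take 9 × 2 × 3 = 54 Aim 1 trials instead of 5 × 2 × 3 = 30. At six trials a day that is three days per brand instead of two, and section IV.E already raises exhaustion. This stands, and a full grid is not proposed here.
- **Many misses are near-ties.** This also stands: most of the achievable gain is kept on the assumed surface.

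A reader might infer from section III that the plan itself argues for an interaction. It does not. It says that height may matter a great deal, in addition to stiffness; it does not say that the best stiffness changes with height. A reader might also infer that the ANOVA excludes an interaction term. The plan lists no model terms, so all that can be said is that none is named.

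**Conclusion.** The concern holds in a limited form. The design yields the best tested stiffness at the recommended height and the best tested height at that stiffness. It may also yield the best pair, but it cannot show that it has.

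A reader might go further and conclude that the recommended pairs will be wrong. The documents do not support that: they give no interaction size, and with no interaction the stepwise rule is exact apart from measurement error. On the assumed noise-free surface the miss rate runs from 0% to 27–30% as r goes from 0 to 0.6, with about 83–99% of the achievable gain kept when r is 0.2 to 0.6. With noise, the share of misses due to interaction is smaller. All of these figures depend on the assumed quadratic form, the spread of the optimum and the noise level.

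The data remain useful. What lacks support is the claim of a joint optimum.

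**What to change.** **(a) Wording.** In the study-day descriptions for both aims (section IV.C), Potential Benefits (IV.D) and section IV.G, report 'k_opt at the recommended height' and 'h_opt at k_opt'. Do not call the pair the optimum unless it has been checked.

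**(b) A rule for the condition already allowed.** Pre-specify in section IV.E that, where a subject's h_opt is not h_R, the additional condition on Days 2, 4 and 6 is the runner-up stiffness from the stiffness day, run at h_opt. This stays within the daily limits: 4 + 2 = 6 trials in Aim 1, and 2 + 1 = 3 series in Aim 2. Report the within-subject 2 × 2 contrast: runner-up minus k_opt at h_opt, less the same difference at h_R. Each difference is taken within one day, so a constant day shift cancels. Because k_opt was selected on the stiffness day's data, noise alone will tend to shrink its lead at h_opt; report the contrast as a check, with that caveat.

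**What not to do.** Do not estimate a stiffness-by-height term by pooling the five planned cells across subjects. It is confounded with the selection of k_opt and can have the wrong sign.

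**Cost.** The claim becomes more modest. The slot competes with the optional 1 cm height steps, and h_opt must be read before the session ends. Where h_opt equals h_R no check is run, so those pairs keep the conditional label.
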